## 2.4 List the study inclusion criteria.

**Aim 1 - Qualitative Review:** We will sample individuals from 4 groups (n=3/group) including:

- Members of WTV's Subject Matter Advisory Board (SMAB)
- CRAFT trainers or experts
- Counselors working in addictions, or
- Addiction program leaders (Addiction Administrators)

These individuals must be

1. 19 years or older
2. Able and willing to participate in audio recorded focus groups and individual interviews
3. Demonstrates complete understanding of the requirements for participation in the study by reading and signing the consent form

**Aim 2 - Training Intervention:** We aim to enroll 45 participants, meeting the following criteria.

1. Is over 19
2. Lives in the US
3. Working in a counselor-related profession
4. Has not been trained in CRAFT
5. Could provide at least 45 minute individual counselor sessions to at least one CSO (CSO)
6. Counseling work involves clients affected by OUDs, or might if they learned CRAFT
7. Is able and willing to submit the required session audiotapes and participate in the tutorial and training and intervention activities over the course of the 12-week study
8. Reports having access to a computer and smartphone with internet access, email, and word processing capability
9. Demonstrates complete understanding of the requirements for participation in the study by reading and signing the consent form
10. Provides valid locator information to allow research and CRAFT training staff to contact them to schedule study-related appointments
11. Completes the first assessment mock session with our standardized patient (SP) and pre-tutorial surveys

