### **Treatment Conditions:**

**Digital Tutorial (T)** - All participants will continue to have access to tutorial materials throughout the study. Participants assigned to the T condition receive ONLY the tutorial. Afterwards they will be encouraged via weekly emails that are a component of the training program to continue using the resources in the online tutorial to revisit the CRAFT lessons on their own during the 10-week period between post-tutorial follow-up and the final follow-up assessment.

**Digital Tutorial, with training materials (TM)** - Participants assigned to the TM condition will complete the tutorial and then receive access to the additional training materials. They will not receive any feedback or video-calls for coaching. They will be encouraged via weekly emails to continue to learn CRAFT on their own during the 10-week post-tutorial period by using the new resources in the online tutorial and the digital training materials.

**Digital Tutorial, with training materials plus feedback and coaching (TMC)** - Systematic feedback and coaching during the 10-week post-tutorial to final assessment period (12 weeks post-baseline) will be provided to only to the 15 participants assigned to the TMC condition. Participants will be required to submit audio taped sessions with clients. They will be provided with consent-to-audiotape forms that they will need to have the client complete prior to

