#### **4.3 Describe pre-defined criteria for removing participants from the study and the procedures for informing participants of their removal from the study. Include information on the handling of their data and measures to ensure individuals' safety and privacy after ceasing research activities.**

We do not anticipate removing participants from the study, but participants may be removed if:

- a) they break the confidentiality of other participants in the focus group (Aim 1) or clients in audiotapes (Aim 2)
- b) it becomes clear after enrollment that they do not meet the inclusion/exclusion criteria.

Participants will be notified of their removal from the study by the Principal Investigator, [name]. The PI will call the participant to explain the reason for their removal. In addition, a formal letter will be sent to participants via email. Both the phone call and letter will explain the reason for their removal, how their data will be handled, and provide referrals for support, if needed.

If any participants are removed due to breaking confidentiality during the 10-week post tutorial period when client audio tapes are submitted, we would use the data they had provided up to that point. Any participants who are removed because it is discovered that they do not meet the inclusion/exclusion criteria will have their data deleted and will not be included for analysis. All contact information will be deleted within two weeks after informing the participant of their removal. We will track and document all reasons for removing participants in order to ensure they are not rescreened and re-enrolled into the study.

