**Describe where the data study, identifiers, and key will be stored, and state the retention period:**

1. Participants will be assigned an identification number which will be affixed to all collected data. Linkage between participant identity and identification numbers will be stored in a password protected electronic file on a secure network drive at Public Health Management Corporation accessible only by key study staff.
2. Participant enrollment spreadsheet containing identifying information will be sent to WTV via encrypted email and in a password protected spreadsheet. This file will not be connected to study data.
3. Electronic obtained consent forms will be stored in a separate restricted folder located on a secure network drive at Public Health Management Corporation accessible only by key study staff.
4. Identifying data (e.g., informed consent forms), screening data, and survey data will be kept for a period of five years after the end of the pilot study as required by NIH/NIDA and then deleted. The information will enable us to ensure pilot study participants do not enroll in a future full research trial.
5. Contact information will be deleted one year after the end of the pilot study.

Identifiers will be removed or destroyed.

**Describe how identifiable data will be de-identified or destroyed. Include information on how, when, and by whom (by role or position, not by name):**

5 years after study completion, all identifying information will be destroyed by PHMC staff.

Identifiers will not be removed or destroyed.

**Provide the rationale for retaining identifiable data and state the retention period. Include information on how and where the identifiable information will be stored:**

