Cover Page: Statistical Analysis Plan
We The Village Counselor Training Study
NCT05875142
Document Date: 09.26.23

Statistical Analysis Plan

Our statistical analysis focuses on a primary endpoint as well as a number of secondary endpoints of interest. The data derive from questionnaires collected from participants in the study. The final enrollment involved three groups: T – Digital Tutorial Overview, TM – Digital Tutorial Plus Training Materials, and TMC – Digital Tutorial Plus Training Materials Plus Feedback and Coaching, with 15, 16, and 16 subjects enrolled, respectively.

1. **T – Digital Tutorial Overview:** Participants assigned to T were given access to a digital tutorial consisting of a curriculum dashboard for review of 10 modules, including videos, PDFs, text and quizzes, which are to be self-administered over two weeks. Modules remain available during the 10-week post tutorial period. Participants receive weekly contact encouraging engagement in all of the materials available to them.
2. **TM – Digital Tutorial Plus Training Materials:** Participants receive the digital tutorial (T) as described above plus access to 10 modules of digital training materials released weekly over the 10-week post tutorial period for self-study. Participants receive weekly contact encouraging engagement in all of the materials available to them.
3. **TMC – Digital Tutorial Plus Training Materials Plus Feedback and Coaching:** Participants receive the digital tutorial (T) plus the digital Training materials as described in the two arms above plus they submit audio recordings of sessions with clients and receive feedback on their application of CRAFT and coaching on how to improve. Participants receive weekly contact encouraging engagement in all of the materials available to them.

Our comparisons are all treatment/control comparisons of T with TM, and T with TMC.

1. Primary Hypothesis
 - 1.1. At 12 weeks (after study start), participants assigned to the TMC condition will demonstrate the highest CRAFT procedure fidelity (measured in audiotaped sessions with a standardized patient) followed by TM and then T.

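### Protocol 4.3 deletes the data of randomised counselors later found ineligible, and neither document confines that judgement to facts fixed before randomisation or keeps it blind to arm and score

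*Protocol*

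**What the plan says.** Protocol 4.3 states that removals are not anticipated, but a participant may be removed on two grounds. Ground (a) is a breach of confidentiality. Ground (b) is that "it becomes clear after enrollment that they do not meet the inclusion/exclusion criteria". The two grounds lead to different handling of data. After a breach during the post-tutorial period, "we would use the data they had provided up to that point". Under ground (b), participants "removed because it is discovered that they do not meet the inclusion/exclusion criteria will have their data deleted and will not be included for analysis". Contact details go within two weeks of notification, and reasons for removal are documented.

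Protocol 4.1 places Aim 2 randomisation after the baseline survey and the baseline mock session.

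Two Aim 2 criteria in Protocol 2.4 concern what a counselor can and will do during the study. Item 5 reads "Could provide at least 45 minute individual counselor sessions to at least one CSO". Item 7, which covers all 12 weeks, reads in part "Is able and willing to submit the required session audiotapes and participate in the tutorial and training and intervention activities over the course of the". Section 3.3 has both answered by self-report at screening.

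Under the treatment conditions in 4.1, the text for TMC says "Participants will be required to submit audio taped sessions with clients", and TMC also has weekly coaching calls. TM has neither feedback nor coaching calls. T has the tutorial and weekly emails.

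The SAP states hypothesis 1.1 by assignment: "participants assigned to the TMC condition will demonstrate the highest CRAFT procedure fidelity". It gives final enrolment as 15 (T), 16 (TM) and 16 (TMC) and plans one-sided t-tests on improvement from baseline to week 12. It names no analysis set and has no rule for removed or missing counselors.

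**The concern.** A comparison of assigned groups is protected by randomisation only while everyone assigned stays in it. An exclusion made afterwards is harmless if it rests on a fact fixed beforehand and is applied without regard to arm or result. Section 4.3 asks for neither. It also does not separate a counselor who was ineligible on entry from one who was eligible and later failed to take part.

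Opportunity to notice a problem differs by arm. Staff hear client tapes and hold weekly calls in TMC; in T and TM they mostly send emails. Section 3.4 says screening answers will not be linked to later data, so a discovery would have to come largely from contact during the study. If counselors removed from TMC would have improved less than their peers, their removal raises the TMC mean, in the direction of the one-sided alternatives. With 16 counselors in the arm, each removal is 1/16, about 6% of it. Once scores are deleted, no sensitivity analysis can use them.

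**Working it through.** **Plan's own figure.** There is none to reproduce. The documents give no alpha, SD, effect size or expected number of removals.

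**Can the rule act after assignment?** Yes. Its trigger is discovery after enrolment (4.3), and randomisation comes straight after the baseline assessments (4.1). The SAP contains nothing that restores a deleted counselor.

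**Whose primary score is at stake?** The primary variable is improvement from baseline to week 12, so both scores are needed.
- Removed after week 12: a complete improvement score is deleted. This is the direct loss.
- Removed before week 12: there is probably no week-12 score. Deletion then costs the baseline and any post-tutorial data, and the counselor leaves the primary comparison either way.

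**Illustrative size.** Inputs from the SAP: T n = 15, TMC n = 16, one-sided two-sample t-test. Assumed: no true effect, improvement SD 1, alpha 0.05, and removal of the k TMC counselors lowest on an engagement score e. Improvement is y = rho × e + sqrt(1 − rho²) × noise. Nobody is removed from T. Each setting used 100,000 simulated trials; the Monte Carlo standard error near 5% is sqrt(0.05 × 0.95 / 100,000) = 0.0007, or 0.07 percentage points.

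| rho | k | Bias toward TMC (SD) | One-sided false-positive rate |
|---|---|---|---|
| 0 | 1 | 0.001 | 5.0% |
| 0.3 | 0 | 0.002 | 5.0% |
| 0.3 | 1 | 0.036 | 6.1% |
| 0.5 | 1 | 0.059 | 6.9% |
| 0.7 | 1 | 0.082 | 8.0% |
| 0.3 | 2 | 0.066 | 7.1% |
| 0.5 | 2 | 0.108 | 9.0% |
| 0.7 | 2 | 0.152 | 11.4% |

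**Hand check of the bias for k = 1.** The expected lowest of 16 standard normal values is −1.766. Removing it raises the mean e of the other 15 by 1.766 / 15 = 0.118. Multiplying by rho gives 0.3 × 0.118 = 0.035, 0.5 × 0.118 = 0.059 and 0.7 × 0.118 = 0.082, which agrees with the simulation. This bias arises only in the TMC mean, so under the same assumptions it would also apply to TMC against TM. The false-positive rate for that pair was not simulated.

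**Retention.** Protocol 8.3 says "survey data will be kept for a period of five years after the end of the pilot study as required by NIH/NIDA". That item lists identifying, screening and survey data. It does not list coded fidelity scores, which are the primary outcome, so its overlap with the deletion rule is partial.

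**The case against.** A reader might infer that TMC counselors who find no CSO or send no client tapes will be judged to fail item 5 or 7 and lose valid scores, while identical T counselors are counted. The documents do not support that.

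- Items 5 and 7 describe capacity and willingness at entry. No passage makes missing tapes or missing CSOs a ground for removal. The protocol caps the number of tapes at 12 and sets no minimum.
- For TMC counselors who struggle to find CSOs, Protocol 9.3 offers help with a client match. The stated response is support.
- Every arm reports its CSO numbers at week 12 (Protocol 4.2), so a T or TM counselor with none would also become visible. Item 7 covers tutorial and training activities, which exist in all arms.
- Losing a complete primary score requires removal after the last assessment, when there is little left to be removed from.
- The simulation removes exactly the least engaged TMC counselors and nobody else. A lack of CSOs may reflect work setting and have nothing to do with engagement.
- Removal reasons are documented, so removals could be counted and bounding analyses run without the scores.

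All of this stands, and it reduces the point to a conditional one. It does not remove it. Section 4.3 still permits post-randomisation exclusion with deletion and does not say what counts as ineligibility. It also keeps data after a confidentiality breach, so removal does not in itself require deletion. The client match helps with item 5 but not with unwillingness to tape or take part.

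**Conclusion.** The point holds in conditional form. The deletion rule can break the comparison of assigned groups, and neither document limits it to pre-randomisation facts or to blinded judgement. Closer contact means that ineligibility may be noticed more often in TMC; the documents do not show that it will be. They report no removal, and the true number may be zero, in which case there is no effect.

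If one TMC counselor were removed for reasons related to outcome, the false-positive rate for TMC over T would rise from 5% to about 6-8%, with a bias of about 0.04 to 0.08 SD. These figures rest on an assumed one-sided alpha of 0.05, an assumed rho of 0.3 to 0.7, no removals in T, and removal of the least engaged counselor. At rho 0 the bias is nil. The overlap with five-year retention in 8.3 is a minor wording matter. The correction is worth making chiefly because it costs almost nothing.

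**What to change.** **Protocol 4.3.** Replace deletion with this: data already collected from a randomised counselor later found ineligible are retained and analysed in the assigned condition, unless the counselor withdraws consent. Add that failing to submit client tapes, to find a CSO or to complete training after randomisation is non-adherence and does not count as ineligibility.

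**SAP.** Define the primary analysis set as all randomised counselors by assigned condition (15, 16, 16). Allow an optional sensitivity analysis that leaves out only those who failed a criterion fixed before randomisation, such as having had earlier CRAFT training, judged blind to arm and score. Report the number of removals and the reasons by arm, including when the number is zero. Retention does not supply a week-12 score for a counselor who left earlier, so the SAP should also say how such counselors are handled.

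**Protocol 8.3.** Align the five-year retention statement with 4.3.

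**Cost.** A short protocol amendment and a few sentences in the SAP, with no added participants or procedures. The downside is that a truly ineligible counselor may slightly dilute the contrast; the sensitivity analysis would show by how much.

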**Aim 2 - Training Intervention:** When a prospective participant responds to a recruitment message, flyer, or referral, they will be directed to visit the We the Village Counselor Training study webpage. On the study website, prospective participants will have the opportunity to read a description of the study, including goals and expectations. If individuals are still interested, they will be directed to click the Screening Survey link. The link will take them directly to the start of the Screening Survey. The Screening Survey is a self-administered multiple choice online Alchemer tool. Potential participants will be asked screening questions to confirm their year of birth, interest in learning CRAFT, that they are working in a counselor-related profession, could provide 45 minute sessions of individual counseling sessions to at least one CSO client, work or could work with clients affected by OUD, have no previous training in CRAFT, are able and willing to submit the required session audiotapes and participate in the training activities over the 12-week study period, have access to a computer or smartphone with internet access, email and word processing capabilities, and reside in the United States. We will program automated scoring to inform participants immediately after filling out the screening survey if they are eligible, unless their answers are not clearly eligible or ineligible. If the results of their screening survey are indeterminate, they will receive a message to call the study number to speak with a study staff person or fill out a contact form to request a call.

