In addition to providing training in the informed consent procedure, counselors will be trained in procedures to protect the confidentiality of the audiotaped sessions. They will be trained to ask clients to avoid using names and instead to refer to the IP in terms of their relationship (e.g., my son, my partner). Sessions will be taped using one of three procedures. First, if the counselor has access to a HIPAA compliant electronic patient health platform that supports audio recording sessions (e.g., SimplePractice) and securely transmitting them (e.g., via encryption), we will accept use of their established system. Second, if their practice does not provide this type of software, we will have counselors download free software (i.e., Pocket Dictate Mobile Dictation Recorder) that allows them to audiotape the session on their telephone and send the encrypted recording to us. Counselors will be instructed to delete the recording immediately after receiving confirmation of receipt. As an additional precaution, they will be shown how to adjust the application settings so that the audio recordings are automatically deleted after 24 hours and instructed to password protect their phone so that only they can access it. Third, if the counselor does not have access to either a HIPAA compliant electronic patient health platform or a smartphone, we will provide them with a digital audio recorder that allows them to securely upload files directly to a HIPAA-compliant server. They will be instructed to delete the audio recording from the device immediately after uploading to this system.

Participants will digitally receive written feedback and live video-call coaching on their tapes (up to 12 allowed). They will be encouraged to re-submit their audio taped sessions until they meet the criteria needed for certification in the CRAFT procedure or until the phase is over (whichever occurs first).

[figure not shown]

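### Deleting the data of counselors found ineligible after randomisation can bias the TMC comparisons, because such discovery is somewhat more likely in TMC

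*Protocol*

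**What the plan says.** Protocol 4.3 gives two grounds for removal. One is a breach of confidentiality. The other applies if "it becomes clear after enrollment that they do not meet the inclusion/exclusion criteria". The two are handled differently. After a breach in the period when client tapes are submitted, "we would use the data they had provided up to that point". Those removed because they "do not meet the inclusion/exclusion criteria will have their data deleted and will not be included for analysis" leave nothing behind. For everyone removed, contact information is deleted within two weeks of notification, and the reasons for removal are to be tracked. The section states that removals are not anticipated.

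Eligibility is self-reported in an online survey (Protocol 3.3). Randomisation follows the baseline survey and mock session (Protocol 4.1). After that, contact differs by arm. In TMC, "Participants will be required to submit audio taped sessions with clients", CRAFT trainers review the tapes, and there is a weekly 30-minute coaching call. TM receives materials and weekly emails without feedback or calls. T receives the tutorial and weekly emails.

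The SAP reports enrolment of 15 (T), 16 (TM) and 16 (TMC) and compares improvement from baseline to week 12 with one-sided t-tests. It states no alpha, defines no analysis population, and does not mention removals or a sensitivity analysis.

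**The concern.** Randomisation protects a comparison only while membership of the analysed groups does not depend on anything that follows assignment. The deletion rule acts on ineligibility found at any time after enrolment, and the opportunity to find it is not the same in each arm. A trainer who hears a counselor's client sessions and speaks with that counselor weekly has more occasions to learn of a disqualifying fact than anyone has in T or TM. If such counselors are dropped from TMC while similar ones stay in the other arms, the analysed groups differ for a reason other than training.

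Deletion makes this worse than ordinary exclusion. Once the data are gone, no all-randomised analysis can be run to see whether the removals mattered. With 16 counselors in TMC, each removal is 1/16, or 6.25%, of the arm.

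**Working it through.** The documents give no removal rate, power or alpha, so there is no figure of the plan's own to reproduce. The check asks how large the effect would be under stated assumptions.

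**Inputs from the documents:** T n = 15 and TMC n = 16; outcome is improvement to week 12; one-sided independent-samples t-test (SAP).

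**Assumptions:** one-sided alpha 0.05; no true training effect; normal scores with SD 1; complete outcome data; k ineligible counselors in each arm whose mean improvement is lower by d SD; all k found and deleted in TMC, none in T. This is the full extreme of arm-dependent discovery.

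**Formula:** after deletion the TMC mean is 0, while the T mean is -k·d/15. The spurious TMC advantage is therefore k·d/15. For k = 2 and d = 1 this is 2 × 1/15 = 0.133 SD.

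**Results (40,000 simulated trials per case):**

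| Removed (k) | Deficit d (SD) | k·d/15 | Simulated shift | Type I error |
|---|---|---|---|---|
| 1 | 0.5 | 0.033 | 0.033 | 6.0% |
| 1 | 1.0 | 0.067 | 0.068 | 6.7% |
| 1 | 1.5 | 0.100 | 0.096 | 7.3% |
| 2 | 0.5 | 0.067 | 0.067 | 6.8% |
| 2 | 1.0 | 0.133 | 0.131 | 9.0% |
| 2 | 1.5 | 0.200 | 0.199 | 10.8% |

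**Direction.** If those removed would have improved 1 SD more (d = -1), the shift is -0.067 SD for one removal and -0.134 SD for two, and type I error falls to 3.1% and 2.0%. The sign depends on who is removed.

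**Upper bound.** Deleting exactly the lowest one or two of 16 TMC scores shifts the TMC mean by 0.12 or 0.22 SD and gives type I error of about 10% or 16%. If removal is only moderately related to the score (correlation 0.5), the shifts are 0.06 or 0.11 SD and the error is about 7% or 9%, in line with the table.

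**After the fix.** With everyone kept, for the same k and d, type I error is 4.1-4.8% (k = 1) or 3.5-5.0% (k = 2), at or below nominal. Removal that works equally in both arms gives a shift of about zero and 4.7-5.1%. The harm comes from unequal discovery.

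**The case against.** The strongest reply is that the documents offer few concrete routes from TMC activity to deletion. Much of this stands.

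- A reader might infer that a TMC counselor who cannot find a client would be deleted. Criterion 5 in Protocol 2.4 asks only that the counselor could provide sessions to a CSO, and Protocol 9.3 offers TMC counselors help with a client match.
- A reader might infer that failing to submit tapes shows ineligibility under criterion 7, "Is able and willing to submit the required session audiotapes and participate in the tutorial and training and intervention activities". That ability and willingness is asked about at screening, and non-submission is not among the removal grounds in 4.3.
- A reader might point to devices: criterion 8 says "Reports having access to a computer and smartphone with internet access" while screening asks whether counselors "have access to a computer or smartphone with internet access". Yet for a TMC counselor who "does not have access to either a HIPAA compliant electronic patient health platform or a smartphone", the Protocol's answer is to supply a recorder, not to remove. The mismatch is a separate wording point.
- Discovery in T and TM is not ruled out. Every arm has live standardized-patient sessions at weeks 2 and 12 and a 12-week question on CSO caseload. Most other criteria, such as age, residence and profession, are facts fixed before randomisation.
- Removal for a confidentiality breach is a different rule that keeps the data collected, and nothing links a breach to low CRAFT skill.

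Two stronger conclusions therefore lack support: that ineligibility is far likelier to be found in TMC, and that the bias must favour TMC. Prior CRAFT training, which a coach might well notice, could push the result either way.

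What the reply does not answer is the rule itself. It can act after randomisation, discovery is not equal across arms, and deletion is irreversible. That removals are not anticipated does not justify the rule; if they are rare, dropping it costs almost nothing.

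**Conclusion.** The point holds as a cheap improvement. The deletion rule in Protocol 4.3 allows exclusion after randomisation that can depend on arm, and the SAP does not correct it. The documents support discovery being somewhat more likely in TMC, and a bias whose direction depends on who is removed. For one or two TMC-only removals of counselors improving 0.5 to 1.5 SD less, one-sided type I error would be about 6-7% or 7-11% instead of 5%. The 10% and 16% figures are a ceiling, because removal under 4.3 does not depend on the 12-week score.

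The number removed, their deficit, the alpha and the absence of any removal from T are all assumptions. The documents do not show that anyone was removed, or whether the 15/16/16 enrolment is counted before or after removals, so nothing here says that the trial's result is biased.

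**What to change.** Replace the deletion sentence in Protocol 4.3, and state the matching analysis population in the SAP:

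- Every randomised counselor is analysed in the assigned arm.
- Research data are kept after later-found ineligibility and deleted only if the participant withdraws consent to their use.
- Exclusion for ineligibility is allowed only as a sensitivity analysis, based on facts fixed before randomisation and judged blind to arm and outcome.
- Removals and their reasons are reported by arm. Protocol 4.3 already requires the reasons to be tracked.
- If follow-up is still open, removed counselors are invited to the 12-week standardized-patient session and survey. The two-week contact-deletion sentence must then be amended, or the invitation cannot be made. The SAP is written in the past tense with final enrolment, so this may no longer be possible; reporting removals by arm would still be.

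The cost is wording in both documents and, where follow-up is open, one standardized-patient session and survey per removed counselor. The downside is that a few ineligible counselors kept in the analysis may slightly dilute the effect.
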